### **8.3. Patient Withdrawal Criteria**

All patients are free to withdraw from participation in the study at any time, for any reason, and without prejudice. The Investigator must withdraw any patient from the study if the patient requests to stop participating in the study. The Investigator, Sponsor, or its designee may remove a patient from the study at any time and for any reason. In addition, patients should be withdrawn if they:

- Experience an intolerable adverse event, including but not limited to, an adverse event  $\geq$  Grade 4, including bone marrow-related events, or a  $\geq$  Grade 3 cardiac event, according to CTCAE v4.0 criteria
- Require a medication that is prohibited by the protocol
- Do not follow guidelines specified in the protocol (ie, is noncompliant with protocol procedures or study treatment administration)
- Any medically appropriate reason or significant protocol violation, in the opinion of the Investigator
- Are lost to follow up

Patients who withdraw or are withdrawn from the study will not be replaced.

#### **8.3.1. Patient Withdrawal Procedures**

A patient who prematurely discontinues study treatment/study participation should have all Week 24 assessments performed as an Early Termination Visit, and return for the Safety Follow-up Visit. The Safety Follow-Up Visit may be waived by the Sponsor in instances where patients have discontinued dosing prior to the Early Termination Visit on a case-by-case basis.

If a patient terminates early from the study, the Investigator will record the reason(s) for early termination on the relevant electronic case report form (eCRF). The specific reason for the withdrawal should be carefully documented on the eCRF.

Patients who require a dose interruption lasting more than 21 days should be discontinued from the study. Adverse events resulting in patient early termination will be followed to the satisfactory resolution and determination of outcome, as ascertained by the Investigator (and/or Sponsor, or its designee); See [Section 11.1.2: Adverse Events](#). The data will be recorded on the appropriate eCRF.

#### **8.4. Emergency Unblinding of Treatment Assignment**

In the case of a medical requirement to break the blind to determine appropriate treatment for an adverse event, unblinding of a patient's treatment assignment can be achieved through the study-specific Interactive Web Response System. If possible, the Investigator should discuss the circumstances with the Medical Monitor prior to accessing unblinding information. In the event of a blind break, the Medical Monitor will be notified through the electronic data capture system. The patient for whom the blind is broken should be subsequently withdrawn from the study. The details regarding the process of breaking the blind are outlined in the Pharmacy Manual.

#### **8.5. Criteria for Study Termination**

If the DMC determines that treatment with CTP-543 poses an unjustified risk to patients, the study may be terminated. The Sponsor reserves the right to discontinue the study at any time for clinical or administrative reasons.

The DMC will review collective safety data for each cohort at regular intervals throughout the study. Should safety signals arise that suggest treatment with CTP-543 poses an unjustified risk to patients, termination of the study or modification of dosing arms may occur upon Sponsor review of the DMC recommendation. The DMC may call for unscheduled data review meetings at any time to ensure appropriate safety monitoring.

Events that would trigger an unscheduled review may include, but are not limited to:

- High frequency of dose interruptions
- High frequency of, or a trend in, SAEs
- High frequency of Grade 3/4 adverse events
- Trend in organ system-specific moderate and/or severe adverse events
- High frequency of patient withdrawal due to adverse events

The Sponsor will notify Investigators of any recommendation of study termination by the DMC. The Sponsor will notify Investigators of recommendation for study modification as necessary to protect patient safety including appropriate instructions for removing patients from treatment, while maintaining the blind.

Any termination required by the Sponsor must be implemented by the Investigator, if instructed to do so, in a time frame that is compatible with the patient's well-being.

## 9. DESCRIPTION OF STUDY TREATMENTS

### 9.1. Description of Treatments

For each cohort, patients will be stratified by alopecia areata subtype and randomized to CTP-543 or placebo in a 2:1 ratio for Cohorts 1 and 2, and 5:1 ratio for Cohort 3.

Treatments arms for each cohort will include:

- Cohort 1
  - CTP-543 4 mg every 12 hours
  - Placebo every 12 hours

If the DMC review of safety parameters for all patients in Cohort 1 (4 mg BID) through Week 12 indicates no safety concerns, Cohort 2 (8 mg BID) will be initiated.

- Cohort 2
  - CTP-543 8 mg every 12 hours
  - Placebo every 12 hours
- If the DMC review of safety parameters for all patients in Cohort 2 (8 mg BID) through Week 12 indicates no safety concerns, Cohort 3 (12 mg BID) will be initiated.
- Cohort 3
  - CTP-543 12 mg every 12 hours
  - Placebo every 12 hours

For each cohort, patients will take the first dose of study drug in the clinic on Day 1 of the Treatment Period and will be instructed to take study drug every 12 hours for the duration of the period. Patients should dose study drug in the clinic on all Study Visit Days after clinical laboratory blood draws are completed.

### 9.2. Dose-Adjustment Criteria

No individualized dose adjustment is allowed during the Treatment Period except in the event of intolerability, for which a dose interruption or study discontinuation may occur at the discretion of the Investigator (see [Section 9.2.1](#) below for details).

The DMC will review collective safety data throughout the study in accordance with the DMC Charter. If the DMC determines a cohort's CTP-543 treatment arm should be stopped, patients receiving treatment at that dose will move to the next lower cohort's CTP-543 treatment arm in a blinded fashion at the patient's next visit, if a lower CTP-543 treatment is available. If a lower CTP-543 treatment arm is not available, the study will terminate. If an immediate hazard is suspected, patients without an imminent visit may have an *Unscheduled Visit* for potential dose adjustment to maintain the blind. In the event of CTP-543 treatment arm cessation and cohort dose adjustment to a lower CTP-543 treatment, the blind will be maintained and individual patient treatment modifications will not be disclosed.

### 9.2.1. Dose Interruption Safety Criteria and Management

Patients who experience hematologic adverse events as described in Table 3 or adverse events that may reflect an unfavorable risk-benefit profile may have their dose interrupted at the discretion of the Investigator. The Medical Monitor should be consulted whenever possible prior to decisions for dose interruption.

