**Patients who require a dose interruption lasting more than 21 days will be discontinued from the study.**

Patients who are discontinued from the study should undergo an Early Termination Visit and subsequent Safety Follow-up Visit as appropriate per Section 8.3.1 Patient Withdrawal Procedures, and associated adverse events followed as described in Section 11 Adverse Events.

In each cohort, hematology parameters will be assessed every 2 weeks for the first 8 weeks of the Treatment Period, and every 4 weeks thereafter for the remainder of each Period. Prior to dose interruption, hematology parameters should be confirmed with repeat testing at an Unscheduled Visit within 72 hours, except in severe cases (i.e.: neutrophil counts below  $0.5 \times 10^9/L$ ) where immediate interruption of dosing is necessary for the safety of the patient. **Blood draws confirming dose interruption criteria should occur prior to the first daily dose on the day of draw.**

Dose interruption requirements for hematologic abnormalities are provided below. However, less significant changes may warrant clinical intervention and the Investigator should use his/her best clinical judgment when considering a dose interruption whether for singular or aggregate hematology results above the limits provided in Table 3, or for other clinical signs, symptoms, or considerations that suggest dose interruption is in the best interest of the patient.

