**Table 3: Selected Hematologic Thresholds for Dose Interruption**

Neutrophil Count	Dose Adjustment
Between $0.5$ to $1 \times 10^9/L$ (Grade 3)	Interrupt dose until recovered to greater than $1.5 \times 10^9/L$ and resume dosing at previous dose
Less than $0.5 \times 10^9/L$ (Grade 4)	Severe case: Interrupt dose immediately and repeat CBC with differential within 72 hours. Recommend hematology consult and contact medical monitor. Patient discontinuation from the study should occur upon repeat confirmation
Female Hemoglobin Level	Dose Adjustment
Less than 10 g/dL	Interrupt dose until recovered to greater than 11.0 g/dL and resume dosing at previous dose
Male Hemoglobin Level	Dose Adjustment
Less than 11.5 g/dL	Interrupt dose until recovered to greater than 12.5 g/dL and resume dosing at previous dose
Platelet Count	Dose Adjustment
Less than $75 \times 10^9/L$	Interrupt dose until recovered to greater than $120 \times 10^9/L$ and resume dosing at previous dose

Upon dose interruption, the parameters that triggered the interruption should be monitored at least weekly until either: 1) recovery above the threshold for dosing resumption is achieved, or 2)

the allowable 21-day dose interruption period has elapsed. In the case of severe neutropenia (neutrophil counts less than  $0.5 \times 10^9/L$ ) patients should discontinue the study and receive instructions to seek medical help if they develop fever or signs of infection. Patients who discontinue the study due to lack of acceptable recovery of parameters within the 21-day dose interruption period should continue to be monitored as appropriate through acceptable clinical resolution.

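### Protocol 9.2.1 makes interruption for a confirmed Table 3 result below Grade 4 both discretionary and required, and weekly counts and the 21-day limit apply only if dosing is interrupted

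*Protocol*

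**What the plan says.** Two places in the Protocol use permissive wording. Section 9.2 bars individual dose adjustment except for intolerability, for which "a dose interruption or study discontinuation may occur at the discretion of the Investigator", and refers to 9.2.1 for details. The first sentence of 9.2.1 covers patients with hematologic adverse events of the kind listed in Table 3, or with other events that may make the risk-benefit balance unfavorable. It says they "may have their dose interrupted at the discretion of the Investigator".

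Later text in 9.2.1 is mandatory. It introduces the table with "Dose interruption requirements for hematologic abnormalities are provided below", and it asks the Investigator to use "best clinical judgment when considering a dose interruption whether for singular or aggregate hematology results above the limits provided in Table 3", so judgment applies to results that have not reached the limits. Each Table 3 row is an instruction. The row for female hemoglobin below 10 g/dL, for example, reads "Interrupt dose until recovered to greater than 11.0 g/dL and resume dosing at previous dose".

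Three further rules in 9.2.1 bear on the point:

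- Confirmation: "Prior to dose interruption, hematology parameters should be confirmed with repeat testing at an Unscheduled Visit within 72 hours", with an exception for severe cases such as neutrophils below 0.5 x 10^9/L.
- Monitoring: "Upon dose interruption, the parameters that triggered the interruption should be monitored at least weekly", until recovery or until the 21-day allowance has run out.
- Time limit: "Patients who require a dose interruption lasting more than 21 days will be discontinued from the study".

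**The concern.** The opening sentence names the Table 3 events and leaves interruption to the Investigator; the text that follows requires it. An Investigator who keeps a patient on drug after a confirmed threshold result can cite the first sentence, and a monitor could not say whether that is a deviation.

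The stake is patient safety, because both safeguards depend on the interruption itself. Weekly counts start when dosing is interrupted, and the 21-day rule measures the length of an interruption. A patient who meets a threshold but continues dosing has neither. The risk is relevant to this drug: it is a deuterated form of ruxolitinib, and Protocol 4.4.1 reports Grade 4 neutropenia as ruxolitinib's dose-limiting toxicity in the multiple-dose study, with label warnings for thrombocytopenia, anemia and neutropenia.

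**Working it through.** **Scope.** Grade 4 neutropenia has its own rule in Table 3 (interrupt at once, repeat the count, discontinue if confirmed), and Protocol 8.3 says patients with other marrow events of Grade 4 or higher should be withdrawn. The conflict is therefore limited to confirmed results below Grade 4 that meet one of these limits:

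- neutrophils 0.5 to 1 x 10^9/L
- hemoglobin below 10 g/dL in women or below 11.5 g/dL in men
- platelets below 75 x 10^9/L

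**The two readings.**

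| | Discretionary (9.2.1, first sentence) | Required (rest of 9.2.1, Table 3) |
|---|---|---|
| Dosing after confirmation | May continue | Stops until recovery |
| Counts | Scheduled visits only | At least weekly |
| Time limit | None | Discontinue if interruption exceeds 21 days |

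**Inputs.** Dosing is every 12 hours, or 2 doses a day (Protocol 9.1). The Schedule of Events places on-treatment counts at Weeks 2, 4, 6, 8, 12, 16, 20 and 24, with visit windows of ±3 days. The confirmatory repeat is due within 72 hours (9.2.1). Doses before confirmation are left out because they are taken under either reading.

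**Interval from a repeat at 72 hours to the next scheduled count, if dosing continues.** Interval = visit spacing − 3 days; doses = 2 × days. At the window extremes (one visit 3 days early, the next 3 days late), add 6 days.

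| Result at | Nominal | Window extremes |
|---|---|---|
| Weeks 2–6 (14-day spacing) | 14 − 3 = 11 days, 22 doses | 14 + 6 − 3 = 17 days, 34 doses |
| Weeks 8–20 (28-day spacing) | 28 − 3 = 25 days, 50 doses | 28 + 6 − 3 = 31 days, 62 doses |

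Each day by which the repeat comes earlier than 72 hours adds 1 day and 2 doses.

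**Same intervals under required interruption.** No doses are taken until recovery. If there is no recovery, weekly counts fall by Days 7, 14 and 21: at least 1 within 11 days, 2 within 17 days, and 3 within 25 or 31 days.

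**Against the 21-day limit.** From Week 8 both intervals exceed it (25 > 21 and 31 > 21). A patient who would have been withdrawn for non-recovery under the required reading could still be dosing under the other, with no new scheduled count.

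**Reach.** Assume 150 randomized.

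- Equal active arms of size a: 1.5a + 1.5a + 1.2a = 150, so a = 35.7 and Cohort 3 = 1.2 × 35.7 = 42.9.
- Equal cohorts: 150 / 3 = 50.

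So Cohort 3 has about 43 to 50 patients, of whom 5/6 (about 36 to 42) receive active drug. The Synopsis estimates last completion in July 2019. Counting back 28 weeks from 1 July gives 17 December 2018; 24 weeks from 31 July gives 13 February 2019. Cohort 3 enrollment would thus have ended around the date of Amendment 5 (21 January 2019).

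**The case against.** The strongest reply is that the section resolves itself when read as a whole. Section 9.2 bans dose adjustment, so the permissive verb in 9.2.1 can be read simply as lifting that ban, with the specific rules following. Section 7.1, the Synopsis and SAP 2.2 all describe interruption for significant cytopenias in mandatory terms. Section 9.2 speaks of intolerability and does not mention laboratory thresholds.

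Other duties also remain for a patient kept on drug:

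- The Medical Monitor should be consulted before interruption decisions where possible (9.2.1).
- A result judged clinically significant should be investigated and repeated (10.11).
- Unscheduled Visits are available (10.13).
- Adverse events must be followed, with further laboratory testing where indicated (11.1.3).
- The DMC continues to review safety data.

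Finally, the long intervals require an Investigator to read past the mandatory text and no other test to intervene.

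Most of this stands. Required interruption is probably what was meant, the remaining duties reduce the risk, and the intervals are worst cases. But the first sentence is not a general permission: it names the Table 3 events and adds Investigator discretion. No text says which wording prevails, and none of the other duties sets a weekly count or a time limit without an interruption. The case against changing 9.2 is fair; aligning it is tidying and not essential.

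**Conclusion.** The concern holds. For confirmed results below Grade 4, Protocol 9.2.1 states two incompatible rules, and following the first literally removes weekly counts and the 21-day limit. The consequence is at worst an 11-day (22-dose) or 25-day (50-dose) interval to the next scheduled count, or 17 or 31 days at the window extremes. This assumes a repeat at 72 hours, full dosing and no intervening test.

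The documents give no rate of Table 3 events, so the number of patients affected cannot be estimated. A correction would reach at most the Cohort 3 patients still on treatment, a number not stated; the whole-cohort figure of about 43 to 50 is only an upper bound and includes placebo patients. No efficacy endpoint or analysis is affected. The change should be made because the wording bears on a safety rule and is simple to correct.

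**What to change.** Reword the first sentence of 9.2.1 to say that:

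- a confirmed result meeting a Table 3 threshold must lead to interruption as the table specifies;
- for neutrophils below 0.5 x 10^9/L, interruption is immediate and does not wait for confirmation;
- interruption is at the Investigator's discretion only for other adverse events and for results that do not reach the Table 3 limits.

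Optionally, bring the discretion wording in 9.2 into line. This adopts the rule that the rest of 9.2.1 and Table 3 already indicate.

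The cost is a short amendment, IRB approval before implementation (Protocol 13.4) and notice to sites. Visits, assessments and analyses stay as they are.

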**Patients who require a dose interruption lasting more than 21 days will be discontinued from the study.**

Patients who are discontinued from the study should undergo an Early Termination Visit and subsequent Safety Follow-up Visit as appropriate per Section 8.3.1 Patient Withdrawal Procedures, and associated adverse events followed as described in Section 11 Adverse Events.

In each cohort, hematology parameters will be assessed every 2 weeks for the first 8 weeks of the Treatment Period, and every 4 weeks thereafter for the remainder of each Period. Prior to dose interruption, hematology parameters should be confirmed with repeat testing at an Unscheduled Visit within 72 hours, except in severe cases (i.e.: neutrophil counts below  $0.5 \times 10^9/L$ ) where immediate interruption of dosing is necessary for the safety of the patient. **Blood draws confirming dose interruption criteria should occur prior to the first daily dose on the day of draw.**

Dose interruption requirements for hematologic abnormalities are provided below. However, less significant changes may warrant clinical intervention and the Investigator should use his/her best clinical judgment when considering a dose interruption whether for singular or aggregate hematology results above the limits provided in Table 3, or for other clinical signs, symptoms, or considerations that suggest dose interruption is in the best interest of the patient.

**Table 3: Selected Hematologic Thresholds for Dose Interruption**

Neutrophil Count	Dose Adjustment
Between $0.5$ to $1 \times 10^9/L$ (Grade 3)	Interrupt dose until recovered to greater than $1.5 \times 10^9/L$ and resume dosing at previous dose
Less than $0.5 \times 10^9/L$ (Grade 4)	Severe case: Interrupt dose immediately and repeat CBC with differential within 72 hours. Recommend hematology consult and contact medical monitor. Patient discontinuation from the study should occur upon repeat confirmation
Female Hemoglobin Level	Dose Adjustment
Less than 10 g/dL	Interrupt dose until recovered to greater than 11.0 g/dL and resume dosing at previous dose
Male Hemoglobin Level	Dose Adjustment
Less than 11.5 g/dL	Interrupt dose until recovered to greater than 12.5 g/dL and resume dosing at previous dose
Platelet Count	Dose Adjustment
Less than $75 \times 10^9/L$	Interrupt dose until recovered to greater than $120 \times 10^9/L$ and resume dosing at previous dose

Upon dose interruption, the parameters that triggered the interruption should be monitored at least weekly until either: 1) recovery above the threshold for dosing resumption is achieved, or 2)

the allowable 21-day dose interruption period has elapsed. In the case of severe neutropenia (neutrophil counts less than  $0.5 \times 10^9/L$ ) patients should discontinue the study and receive instructions to seek medical help if they develop fever or signs of infection. Patients who discontinue the study due to lack of acceptable recovery of parameters within the 21-day dose interruption period should continue to be monitored as appropriate through acceptable clinical resolution.

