## **11. ADVERSE EVENTS**

### **11.1.1. Definition of Adverse Event**

An adverse event is any untoward medical occurrence that may appear or worsen in a patient during the course of a study. It may be a new intercurrent illness, a worsening concomitant illness, an injury, or any concomitant impairment of the patient's health, including laboratory test values, regardless of etiology. Any worsening (ie, any clinically significant adverse change in the frequency or intensity of a pre-existing condition) should be considered an adverse event. A diagnosis or syndrome should be recorded on the adverse event page of the eCRF rather than the individual signs or symptoms of the diagnosis or syndrome. A worsening of the condition under study, alopecia areata, will not be reported as an adverse event.

All patients will be monitored for adverse events during the study. Assessments may include monitoring of the following parameters: the patient's clinical symptoms, laboratory, physical examination findings, or findings from other tests and/or procedures.

An adverse event reported after informed consent, but before the first dose of study drug (ie, Day 1), will be considered a pretreatment adverse event and will be captured on the eCRF. Adverse events will be considered treatment-emergent if the onset is after the first dose of study drug.

An abnormal laboratory value is considered to be an adverse event if the abnormality:

- results in discontinuation from the study;
- is judged by the Investigator to be of significant clinical importance requiring treatment, modification/interruption of investigational product dose, or any other therapeutic intervention

Regardless of severity grade, only laboratory abnormalities that fulfill a seriousness criterion need to be documented as a serious adverse event.

If a laboratory abnormality is one component of a diagnosis or syndrome, then only the diagnosis or syndrome should be recorded on the adverse event eCRF. If the abnormality was not a part of a diagnosis or syndrome, then the laboratory abnormality should be recorded as the adverse event. If possible, the laboratory abnormality should be recorded as a medical term and not simply as an abnormal laboratory result (e.g., record thrombocytopenia rather than decreased platelets).

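### Protocol Table 3 and section 8.3 give opposite instructions for a Grade 4 platelet or hemoglobin event that recovers within 21 days

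*Protocol*

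**What the plan says.** Table 3 (protocol section 9.2.1) has five rows. Two are for neutrophils, split by grade. The Grade 4 row, below 0.5 × 10⁹/L, ends with "Patient discontinuation from the study should occur upon repeat confirmation". The other three rows are for female hemoglobin (below 10 g/dL), male hemoglobin (below 11.5 g/dL) and platelets (below 75 × 10⁹/L). None of these has a lower limit or a discontinuation branch. For female hemoglobin the action is "Interrupt dose until recovered to greater than 11.0 g/dL and resume dosing at previous dose", and for male hemoglobin "Interrupt dose until recovered to greater than 12.5 g/dL and resume dosing at previous dose". The platelet row has the same form, with recovery to above 120 × 10⁹/L.

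Section 8.3 introduces its list with "In addition, patients should be withdrawn if they". The first item covers intolerable adverse events and names, by CTCAE v4.0, those at or above "Grade 4, including bone marrow-related events". It is not limited to neutrophils.

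Sections 8.3.1 and 9.2.1 discontinue any patient whose interruption lasts more than 21 days. Section 9.2.1 also asks for a repeat blood test within 72 hours before dosing is interrupted, "except in severe cases (i.e.: neutrophil counts below" 0.5 × 10⁹/L).

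**The concern.** A site with a Grade 4 platelet or hemoglobin event that has recovered in time cannot follow both instructions. One site could re-expose its patient at the same dose while another withdraws a patient with the same event. These are the patients with the deepest cytopenias, in an ascending-dose study. Section 4.4.1 lists thrombocytopenia and anemia, with neutropenia, among the labelled warnings of the parent drug.

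Reporting is affected as well. The same event would count under interruption at one site and under discontinuation at another, and both are tabulated by treatment group (protocol section 12.4.6, SAP section 9.2). Withdrawal also changes how the patient's Week 24 SALT value is obtained, because SAP section 8.3.1 carries forward the last on-treatment score when later scores are missing.

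**Working it through.** No statistical figure is involved, so the check sets the rules side by side.

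**Step 1: does a Table 3 value fall within section 8.3?** Under section 11.1.1 an abnormal laboratory value is an adverse event if it "is judged by the Investigator to be of significant clinical importance requiring treatment, modification/interruption of investigational product dose". The severity section of chapter 11 has all events graded by CTCAE v4.0. A low platelet or hemoglobin value judged important enough to require interruption is therefore a graded adverse event, and section 8.3 can apply to it. SAP section 9.3 summarizes Grade 3 and 4 values for neutrophils, platelets and hemoglobin alike, so the trial's own documents treat Grade 4 as a meaningful category for all three.

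**Step 2: compare the actions.**

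| Grade 4 event | Table 3 and section 9.2.1 | Section 8.3 | Result |
|---|---|---|---|
| Neutrophils | Interrupt at once; discontinue when confirmed | Withdraw | Consistent |
| Platelets, recovered above 120 × 10⁹/L within 21 days | Resume at previous dose | Withdraw | Conflict |
| Hemoglobin, recovered above 11.0 g/dL (female) or 12.5 g/dL (male) within 21 days | Resume at previous dose | Withdraw | Conflict |
| Platelets or hemoglobin, not recovered within 21 days | Discontinue | Withdraw | Same outcome |

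Three of the five rows of Table 3 lack a lower limit. The conflict lies only in the part of those rows that is both Grade 4 and recovered in time.

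**Step 3: look for a rule of precedence.** Neither section 8.3 nor section 9.2.1 says that one overrides the other for these events. Table 3 repeats the Grade 4 discontinuation for neutrophils, and the text under it repeats it again for severe neutropenia only. A site could reasonably infer that the other parameters are meant to be handled differently.

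**Step 4: the repeat-test exception.** The exception is introduced with i.e., so on its wording no platelet or hemoglobin value is a severe case. With one dose every 12 hours, the 72-hour limit allows at most 72 / 12 = 6 further doses before confirmation. This is a ceiling, not an expected number.

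**The case against.** The strongest reply is that the passages can be read together. Section 8.3 decides who stays in the study, Table 3 governs the dosing of those who stay, and a withdrawn patient has no dosing to resume. Section 7.1 states the general principle that significant cytopenias are managed by severity, through interruption or discontinuation. On this view only a cross-reference is missing. The reading is possible, but the protocol does not state it. Table 3 weakens it by restating the Grade 4 rule for one parameter and not for the other two.

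Investigator discretion is a second reply. Section 9.2.1 says that dosing may be interrupted at the Investigator's discretion, with the Medical Monitor consulted where possible, and section 8.3 says should. But section 9.2.1 also presents the table as requirements, and its appeal to clinical judgment concerns results above the table's limits or other clinical considerations. Discretion does not say which rule governs resumption. It does carry weight on the secondary point, because an Investigator may stop dosing before a repeat test on other clinical grounds.

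A reader might also infer more than the documents support:

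- **That every Grade 4 platelet or hemoglobin event is in conflict.** The 21-day limit removes all those that do not recover in time.
- **That six doses would typically be given before confirmation.** The 72 hours is an outer limit on a repeat test that should be done, and discretion applies.
- **That the DMC could miss these events.** Section 8.5 lists a high frequency of Grade 3/4 adverse events as a separate trigger for unscheduled review, so that route does not depend on whether a site interrupts or withdraws. It sets no numerical thresholds.
- **That section 4.4.1 calls cytopenia the main risk of the drug class.** It lists cytopenias with infection, skin cancer, lipid elevations and symptom exacerbation for ruxolitinib. The dose-limiting toxicity it names is Grade 4 neutropenia, which Table 3 already handles.

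**Conclusion.** The contradiction is real but narrow. It covers platelet or hemoglobin events that are Grade 4 by CTCAE v4.0 and recover above the Table 3 resumption threshold within 21 days. For these, Table 3 says resume at the previous dose, section 8.3 says withdraw, and no precedence is stated.

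The conclusion rests on two assumptions. First, the Investigator judges the value to be an adverse event under section 11.1.1, which follows when it is held to require interruption. Second, Grade 4 events in these parameters fall below the Table 3 triggers. The documents give no CTCAE cut-offs for platelets or hemoglobin and leave the criteria to the Site Operations Manual, so the values at which the rules collide cannot be stated. Since the rows have no lower limit, the conflict does not depend on the exact figures.

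The number of patients cannot be calculated from the documents and is expected to be small, so any effect on the efficacy comparison should be slight. The reason to act is consistent handling of a few high-risk patients. The neutrophil-only exception in section 9.2.1 is secondary. Nothing in the documents shows which of the two rules is the intended one.

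**What to change.** Reconcile section 8.3, section 9.2.1 and Table 3 so that a single rule applies to Grade 4 platelet and hemoglobin events, including those that recover within 21 days. Cross-reference that rule in both section 8.3 and Table 3. In the same clarification, state whether the severe-case exception to repeat testing is meant to cover neutrophils only, so that its wording agrees with the rule chosen. The sponsor's medical team and the DMC should decide which rule applies; this review takes no position on it.

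The cost is a short protocol clarification, with no new tests, visits or patients. Depending on the choice, a few events may move between the interruption and discontinuation counts.
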